8.3.5 Pregnancy

Please refer to the master protocol.

8.3.6 Cardiovascular and death events

Please refer to the master protocol.

8.3.7 Disease-related events and/or disease-related outcomes not qualifying as AEs or SAEs

Not applicable.

8.3.8 Adverse event of special interest

Please refer to the master protocol.

In addition, symptomatic or asymptomatic overdose with pembrolizumab are described as below:

- An overdose of pembrolizumab will be defined as any dose of 1000 mg or greater.

8.3.9 Guidelines for reporting product complaints

Please refer to the master protocol.

8.4 PHARMACOKINETICS

Please refer to the master protocol for a description of common PK evaluations. Substudy specific evaluations are summarized below.

PK parameters (eg, maximum concentration, area under the concentration time curve) will be generated in patients undergoing intensive PK sampling (as in Section 1.5.1 of the master protocol). Samples collected for analyses of cetuximab concentration may also be used to evaluate safety or efficacy aspects related to concerns arising during or after the study and any remaining plasma/serum volume may also be used for further exploratory analysis if deemed relevant.

8.5 GENETICS AND/OR PHARMACOGENOMICS

Please refer to the master protocol.

8.6 BIOMARKERS

Please refer to the master protocol.

8.7 IMMUNOGENICITY ASSESSMENTS

Please refer to the master protocol.

8.8 HEALTH ECONOMICS

Please refer to the master protocol.

8.9 USE OF BIOLOGICAL SAMPLES AND DATA FOR FUTURE RESEARCH

Please refer to the master protocol.

9 STATISTICAL CONSIDERATIONS

9.1 STATISTICAL HYPOTHESES

Please refer to the master protocol.

9.2 SAMPLE SIZE DETERMINATION

The plan is to treat approximately 40 participants per cohort for Cohorts D1 and D2.

Table 13 lists estimated ORR and 90% exact confidence intervals (CIs) by number of responders from a sample size of 40 participants treated.

Table 13 - Estimated objective response rate (ORR) depending on number of responders

Number of Responders (N=40)	Objective Response Rate in % (90% Clopper-Pearson CI)
2	5% (0.9% - 14.9%)
4	10% (3.5% - 21.4%)
6	15% (6.7% - 27.5%)
8	20% (10.4% - 33.2%)
10	25% (14.2% - 38.7%)
12	30% (18.3% - 44.0%)
14	35% (22.6% - 49.2%)

CI: confidence interval; N=number.

With a sample size of 40 study participants, the probability of observing 1 or more instances of a specific AE with a true incidence rate of 1%, 2%, or 5% is 33.1%, 55.4%, or 87.1%, respectively. This provides reasonable assurance that events occurring at $\geq 5\%$ frequency can be identified in these cohorts.

9.3 POPULATIONS FOR ANALYSES

Please refer to the master protocol.

9.4 STATISTICAL ANALYSES

Please refer to the master protocol.

9.4.1 General considerations

Please refer to the master protocol.

9.4.2 Primary endpoint(s)

Please refer to the master protocol.

9.4.3 Secondary endpoint(s)

Please refer to the master protocol for description of common objectives and endpoints. Substudy-specific objectives and endpoints are summarized below.

9.4.3.1 Other secondary endpoints

Plasma concentrations (or where applicable PK parameters) of cetuximab will be summarized with descriptive statistics.

9.4.4 Tertiary/exploratory endpoint(s)

[REDACTED]

9.4.4.1 Exploratory antitumor indicators

[REDACTED]

9.4.5 Other safety analysis

Please refer to the master protocol.

9.4.6 Other analysis

Please refer to the master protocol.

9.5 INTERIM ANALYSES

Please refer to the master protocol.

For each cohort, if the predictive probability of concluding a minimum clinical meaningful effect of the study treatment (ORR of 5% for both cohorts) at the end of study is <15%, the corresponding cohort will be stopped for futility. To facilitate the calculation of predictive probability, a minimum informative prior of Beta (0.5, 0.5) is used at the time of the design of the study. However, emerging data generated from outside of the study may warrant a different prior to be considered before this interim analysis.

10 SUPPORTING DOCUMENTATION AND OPERATIONAL CONSIDERATIONS

10.1 APPENDIX 1: REGULATORY, ETHICAL, AND STUDY OVERSIGHT CONSIDERATIONS

10.1.1 Regulatory and ethical considerations

Please refer to the master protocol.

10.1.2 Financial disclosure

Please refer to the master protocol.

10.1.3 Informed consent process

Please refer to the master protocol.

10.1.4 Data protection

Please refer to the master protocol.

10.1.5 Committees structure

Please refer to the master protocol.

10.1.6 Dissemination of clinical study data

Please refer to the master protocol.

10.1.7 Data quality assurance

Please refer to the master protocol.

10.1.8 Source documents

Please refer to the master protocol.

10.1.9 Study and site start and closure

Please refer to the master protocol.

10.1.10 Publication policy

Please refer to the master protocol.

10.2 APPENDIX 2: CLINICAL LABORATORY TESTS

Clinical laboratory tests that are common to all cohorts are detailed in the master protocol. Cohort D1 and D2 specific evaluations are presented in [Table 14](#).

Table 14 - Protocol-required laboratory tests

Endocrine function tests ^a	Thyroid-stimulating hormone (TSH) Tri-iodothyronine (T3) Free thyroxine (FT4) Cortisol (preferably in the morning)
---------------------------------------	---

NOTES :

a Endocrine function tests will be performed every 2 cycles throughout the entire treatment period and at EOT in cohorts receiving pembrolizumab. During the Observation Period, they will be performed at Follow-Up Visit 1. They can also be performed as clinically indicated.

In addition, for participants in Cohort D2, electrolytes to be done weekly under treatment and then at the end of treatment, at FU visit 1 and as clinically indicated. After last IMP administration, additional electrolytes monitoring for Cohort D2, outside the visits, may be done according to the local standard institutional care.

10.3 APPENDIX 3: AES AND SAES: DEFINITIONS AND PROCEDURES FOR RECORDING, EVALUATING, FOLLOW-UP, AND REPORTING

Please refer to the master protocol.

10.4 APPENDIX 4: CONTRACEPTIVE AND BARRIER GUIDANCE

Please refer to the master protocol.

10.5 APPENDIX 5: GENETICS

Please refer to the master protocol.

10.6 APPENDIX 6: LIVER AND OTHER SAFETY: SUGGESTED ACTIONS AND FOLLOW-UP ASSESSMENTS

Not applicable.

[figure not shown]
10.7 APPENDIX 7: COUNTRY-SPECIFIC REQUIREMENTS

[figure not shown]
Please refer to the master protocol.

10.8 APPENDIX 8: RESPONSE EVALUATION CRITERIA IN SOLID TUMORS (RECIST) 1.1

Please refer to the master protocol.

10.9 APPENDIX 9: [REDACTED]

10.9.1 Response and stable disease duration (RECIST 1.1 and █)

Response duration will be measured from the time measurement criteria for CR/PR or █ (whichever is first recorded) are first met until the first date that recurrent or PD is objectively documented, taking as reference the smallest measurements recorded on study (including baseline).

Stable disease duration will be measured from the time of start of treatment until the criteria for progression are met, taking as reference the smallest sum on study (including baseline).

10.9.2 Methods of measurement

The same method of assessment and the same technique should be used to characterize each identified and reported lesion at baseline and during follow-up. Assessments should be identified on a calendar schedule and should not be affected by delays in therapy. While on study, all lesions recorded at baseline should have their actual measurements recorded at each subsequent evaluation, even when very small (eg, 2 mm). If it is the opinion of the radiologist that the lesion has likely disappeared, the measurement should be recorded as 0 mm. If the lesion is believed to be present and is faintly seen but too small to measure, a default value of 5 mm should be assigned. For lesions which fragment/split add together the longest diameters of the fragmented portions; for lesions which coalesce, measure the maximal longest diameter for the “merged lesion.”

Clinical Lesions. Clinical lesions will only be considered measurable when they are superficial and ≥ 10 mm as assessed using calipers (eg, skin nodules). For the case of skin lesions, documentation by color photography including a ruler to estimate the size of the lesion is recommended. If feasible, imaging is preferred.

Chest X-Ray. Chest CT is preferred over chest X-ray, particularly when progression is an important endpoint, since CT is more sensitive than X-ray, particularly in identifying new lesions. However, lesions ≥ 20 mm on chest X-ray may be considered measurable if they are clearly defined and surrounded by aerated lung.

CT, MRI. CT is the best currently available and reproducible method to measure lesions selected for response assessment. This guideline has defined measurability of lesions on CT scan based on the assumption that CT slice thickness is 5 mm or less. When CT scans have slice thickness greater than 5 mm, the minimum size for a measurable lesion should be twice the slice thickness. MRI is also acceptable in certain situations (eg, for body scans). Other specialized imaging or other techniques may also be appropriate for individual case. For example, while PET scans are not considered adequate to measure lesions, PET-CT scans may be used providing that the measures are obtained from the CT scan and the CT scan is of identical diagnostic quality to a diagnostic CT (with IV and oral contrast).

Ultrasound. Ultrasound is not useful in assessment of lesion size and should not be used as a method of measurement. If new lesions are identified by ultrasound in the course of the study, confirmation by CT is advised.

Endoscopy, Laparoscopy. The utilization of these techniques for objective tumor evaluation is not advised. However, they can be useful to confirm complete pathological response when biopsies are obtained or to determine relapse in trials where recurrence following complete response or surgical resection is an endpoint.

Tumor Markers. Tumor markers alone cannot be used to assess objective tumor response. If markers are initially above the upper normal limit, however, they must normalize for a patient to be considered in CR.

Cytology, Histology. These techniques can be used to differentiate between PR and CR in rare cases if required by protocol (for example, residual lesions in tumor types such as germ cell tumors, where known residual benign tumors can remain). When effusions are known to be a potential adverse effect of treatment (eg, with certain taxane compounds or angiogenesis inhibitors), the cytological confirmation of the neoplastic origin of any effusion that appears or worsens during treatment when the measurable tumor has met criteria for response or stable disease is advised to differentiate between response or SD and PD.

10.10 APPENDIX 10: CONTINGENCY MEASURES FOR A REGIONAL OR NATIONAL EMERGENCY THAT IS DECLARED BY A GOVERNMENTAL AGENCY

Please refer to the master protocol.

10.11 APPENDIX 11: RISK ASSESSMENT

Please refer to the master protocol for detailed information about SAR444245, available information about pembrolizumab and cetuximab is shown in [Table 15](#).

Table 15 - Risk assessment

Potential risk of clinical significance	Summary of data/rationale for risk	Mitigation strategy
Study intervention(s)		
Infusion reactions	
Pembrolizumab
 
Common, but infusion-related reactions in labeling include drug hypersensitivity, anaphylactic reaction, anaphylactoid reaction, hypersensitivity and cytokine release syndrome.
 
Cetuximab
 
Severe infusion-related reactions, including anaphylactic reactions, may commonly occur, in some cases with fatal outcome. Symptoms may occur during the first infusion and for up to several hours afterwards or with subsequent infusions. Symptoms may include bronchospasm, urticaria, increase or decrease in blood pressure, loss of consciousness or shock. In rare cases, angina pectoris, myocardial infarction or cardiac arrest have been observed.
 
Anaphylactic reactions may occur as early as within a few minutes of the first infusion and can occur despite the use of premedication.
 
The risk for anaphylactic reactions is much increased in patients with a history of allergy to red meat or tick bites or positive results of tests for IgE antibodies against cetuximab (α-1-3-galactose). In these patients cetuximab should be administered only after a careful assessment of benefit/risk, including alternative treatments, and only under close supervision of well-trained personnel with resuscitation equipment ready.
 
A cytokine release syndrome (CRS) typically occurs within one hour after infusion and is less commonly associated with bronchospasm and urticaria. CRS is normally most severe in relation to the first infusion. Mild or moderate infusion-related reactions are very common comprising symptoms such as fever, chills, dizziness, or dyspnea that occur in a close temporal relationship mainly to the first cetuximab infusion
	
Pembrolizumab
 
Dose modification and treatment guidelines for pembrolizumab infusion associated reactions are provided in Table 5.
 
Cetuximab
 
Occurrence of a severe infusion-related reaction requires immediate and permanent discontinuation of cetuximab therapy and may necessitate emergency treatment.
 
It is recommended to warn patients of the possibility of such a late onset and instruct them to contact their physician if symptoms or signs of an infusion-related reaction occur.
 
The first dose should be administered slowly and the speed must not exceed 5 mg/min whilst all vital signs are closely monitored for at least two hours. If during the first infusion, an infusion-related reaction occurs within the first 15 minutes, the infusion should be stopped. A careful benefit/risk assessment should be undertaken including consideration whether the patient may have performed IgE antibodies before a subsequent infusion is given.
 
Premedicate with a histamine-1 (H1) receptor antagonist prior to cetuximab administration. Monitor patients for at least 1 hour following each cetuximab infusion, in a setting with resuscitation equipment and other agents necessary to treat anaphylaxis. Initiate SAR444245 infusion only when no infusion reaction has occurred after 1-2 hours of observation. In patients requiring treatment for infusion reactions, use recommended per the country-approved product labeling (eg, USPI, SmPC) for cetuximab.
 
If an infusion-related reaction develops later during the infusion or at a subsequent infusion further management will depend on its severity:


Potential risk of clinical significance	Summary of data/rationale for risk	Mitigation strategy
	
a) Grade 1: continue slow infusion under close supervision
 
b) Grade 2: continue slow infusion and immediately administer treatment for symptoms
 
c) Grade 3 and 4: stop infusion immediately, treat symptoms vigorously and contraindicate further use of cetuximab
	
Immunogenicity (Anti-drug antibodies)	
Cetuximab
 
The development of human anti-chimeric antibodies (HACA) is a class effect of monoclonal chimeric antibodies. Current data on the development of HACAs is limited. Overall, measurable HACA titers were noted in 3.4% of the patients studied, with incidences ranging from 0% to 9.6% in the target indication studies. No conclusive data on the neutralizing effect of HACAs on cetuximab is available to date. The appearance of HACA did not correlate with the occurrence of hypersensitivity reactions or any other undesirable effect to cetuximab.
	
Hypersensitivity, including anaphylaxis	
Pembrolizumab
 
Not specifically reported but included among infusion-related reactions in label.
 
Cetuximab
 
Please see above within Infusion reactions
	
Exclusion of participants with known hypersensitivity to any components of pembrolizumab.
 
Also, see specific instructions for cetuximab.

Infections	
Pembrolizumab
 
Common: pneumonia.
 
Cetuximab
 
Patients who receive cetuximab in combination with platinum-based chemotherapy are at an increased risk for the occurrence of severe neutropenia, which may lead to subsequent infectious complications such as febrile neutropenia, pneumonia or sepsis. Careful monitoring is recommended in such patients, in particular in those who experience skin
	See routine mitigation in the master protocol.

Potential risk of clinical significance	Summary of data/rationale for risk	Mitigation strategy
	
lesions, mucositis or diarrhea that may facilitate the occurrence of infections.
 
Further, the risk for secondary infections (mainly bacterial) of adverse skin reactions is increased and cases of staphylococcal scalded skin syndrome, necrotizing fasciitis and sepsis, in some cases with fatal outcome, have been reported
	
Hepatotoxicity	
Pembrolizumab
 
Hepatitis occurred in 0.8% of patients, including Grade 2, 3 or 4 cases in 0.1%, 0.5% and 0.1% patients, respectively, receiving pembrolizumab. The median time to onset of hepatitis was 3.6 months (range 8 days to 21.4 months). The median duration was 1.1 months (range 1 day to 20.9+ months). Hepatitis led to discontinuation of pembrolizumab in 0.3% patients. Hepatitis resolved in 36 patients.
 
Cetuximab
 
Increase in liver enzymes is very common
	
Exclusion of participants with impaired liver functions.
 
Monitor clinical signs and symptoms of hepatic impairment as part of TEAE. Monitor liver function parameters (AST, ALT, bilirubin & ALP) regularly from screening and throughout the study.
 
Dose modification and treatment guidelines for liver enzyme increase are provided under immune-related reactions in Table 9.

Nephrotoxicity	
Pembrolizumab
 
Common: nephritis, acute kidney injury
 
Cetuximab
 
Not reported in the SmPC
	
Dose modification and treatment guidelines for nephrotoxicity are provided under immune-related reactions in Table 9.

Hypomagnesaemia	
Cetuximab
 
Hypomagnesaemia is very common
	
Exclusion of participants with electrolytes (magnesium, calcium, potassium) outside the normal ranges.
 
Monitor electrolytes regularly as per protocol.

Neurological AEs	
Pembrolizumab
 
Dizziness, headache, neuropathy peripheral, dysgeusia (very common) and lethargy (common) for pembrolizumab in combination with chemotherapy
 
Uncommon: epilepsy.
 
Cetuximab:
 
Headaches are common
	
Dose modification and treatment guidelines for neurological AEs are provided under immune-related reactions in Table 9.

Cardiovascular effects, including QT interval prolongation	
Cetuximab
 
Cardiopulmonary arrest or sudden death have occurred in 2-3% patients with squamous cell carcinoma of the head and neck receiving cetuximab with radiation therapy or a cetuximab product with platinum-based therapy and fluorouracil cetuximab. A history of coronary artery disease, congestive heart failure, or arrhythmias and abnormal serum electrolytes may be predisposing factors.
	
Specifically, for patients receiving cetuximab, exclude patients with electrolytes (magnesium, calcium and potassium) <LLN and monitor serum electrolytes weekly during and for at least 8 weeks after last cetuximab administration.

Immune-mediated Adverse Events	
Pembrolizumab
 
Immune-mediated adverse events are designated as important identified risk for pembrolizumab.
 
Cetuximab
 
Not reported as such in the SmPC.
	
Dose modification and treatment guidelines for immune-related reactions are provided in Table 9.
 
Patients treated with cetuximab:
 
If a diagnosis of ulcerative keratitis is confirmed, treatment with cetuximab should be

Potential risk of clinical significance	Summary of data/rationale for risk	Mitigation strategy
	
Patients presenting with signs and symptoms suggestive of keratitis such as acute or worsening: eye inflammation, lacrimation, light sensitivity, blurred vision, eye pain and/or red eye should be referred promptly to an ophthalmology specialist.
 
Very rarely, Stevens-Johnson syndrome/toxic epidermal necrolysis may occur in patients treated with cetuximab.
	
interrupted or discontinued. If keratitis is diagnosed, the benefits and risks of continuing treatment should be carefully considered. Cetuximab should be used with caution in patients with a history of keratitis, ulcerative keratitis or severe dry eye. Contact lens use is also a risk factor for keratitis and ulceration.

Interstitial lung disease	
Cases of interstitial lung disease (ILD), including fatal cases, have been reported, with the majority of patients from the Japanese population.
 
Confounding or contributing factors, such as concomitant chemotherapy known to be associated with ILD, and pre-existing pulmonary diseases were frequent in fatal cases.
	
Patients treated with cetuximab: Patients should be closely monitored for ILD. In the event of symptoms (such as dyspnoea, cough, fever) or radiographic findings suggestive of ILD, prompt diagnostic investigation should occur.

Dermatological toxicities	
Pembrolizumab: Refer to immune-related adverse events
 
Cetuximab: Cetuximab can cause dermatologic toxicities, including acneiform rash, skin drying and fissuring, paronychial inflammation, infectious sequelae (for example, S. aureus sepsis, abscess formation, cellulitis, blepharitis, conjunctivitis, keratitis/ulcerative keratitis with decreased visual acuity, cheilitis), and hypertrichosis. Acneiform rash occurred in 82% of patients across clinical trials. Grades 3 or 4 acneiform rash occurred in 9.7% of patients. Acneiform rash usually developed within the first two weeks of therapy; the rash lasted more than 28 days after stopping treatment in most patients. Life-threatening and fatal bullous mucocutaneous disease with blisters, erosions, and skin sloughing, has been observed. It could not be determined whether these mucocutaneous adverse reactions were directly related to EGFR inhibition or to idiosyncratic immune-related effects (eg, Stevens-Johnson syndrome or toxic epidermal necrolysis).
	
For cetuximab:
 
Monitor patients for dermatologic toxicities and infectious sequelae. Instruct patients to limit sun exposure during cetuximab therapy. Withhold, reduce dose or permanently discontinue cetuximab based on severity of acneiform rash or mucocutaneous disease

Risks related to special populations		
Pregnancy and lactation exposure and outcomes	
Pembrolizumab Pembrolizumab should not be used during pregnancy unless the clinical condition of the woman requires treatment with pembrolizumab.
 
Cetuximab EGFR is involved in foetal development. Limited observations in animals are indicative of a placental transfer of cetuximab, and other IgG1 antibodies have been found to cross the placental barrier. Animal data revealed no evidence of teratogenicity. However, dependent on the dose, an increased
	
See master protocol for exclusion of participants, guidance on highly effective contraceptive methods, and pregnancy tests to be performed regularly.
 
It is recommended that women do not breastfeed during treatment with cetuximab and for 2 months after the last dose, because it is not known whether cetuximab is excreted in breast milk.

Potential risk of clinical significance	Summary of data/rationale for risk	Mitigation strategy
	incidence of abortion was observed. Sufficient data from pregnant or lactating women are not available.	
	It is strongly recommended that cetuximab be given during pregnancy or to any woman not employing adequate contraception only if the potential benefit for the mother justifies a potential risk to the foetus.	
	Breast-feeding	
	It is recommended that women do not breast-feed during treatment with cetuximab and for 2 months after the last dose, because it is not known whether cetuximab is excreted in breast milk.	
	Fertility	
	There are no data on the effect of cetuximab on human fertility. Effects on male and female fertility have not been evaluated within formal animal studies.	
Drug-drug interactions	No data available.	
Overdose and its treatment	No specific information is available on the treatment of overdose of pembrolizumab.	See Section 6.8 of the master protocol.

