Grade 3 Prolonged (ie, not rapidly responsive to symptomatic medication and/or brief interruption of infusion); recurrence of symptoms following initial improvement; hospitalization indicated for other clinical sequelae	SAR444245 infusion should be interrupted if applicable. If IRR is clearly attributable to SAR444245, SAR444245 should be permanently discontinued. The participant can continue treatment with the other anti-cancer therapy in combination During or after completion of infusion, additional appropriate medical therapy may include but is not limited to epinephrine ^b , IV fluids, antihistamines, NSAIDs, acetaminophen, narcotics, oxygen, vasopressors, corticosteroids. Increase monitoring of vital signs as medically indicated until the participant recovers.
Grade 4 Life-threatening; pressor or ventilator support indicated	SAR444245 infusion should be interrupted if applicable. If IRR is clearly attributable to SAR444245, SAR444245 should be permanently discontinued. The participant can continue treatment with the other anti-cancer therapy in combination During or after completion of infusion, additional appropriate medical therapy may include but is not limited to epinephrine ^b , IV fluids, antihistamines, NSAIDs, acetaminophen, narcotics, oxygen, vasopressors, corticosteroids. Increase monitoring of vital signs as medically indicated until the participant recovers.

a Information for preparation and storage of SAR444245 are provided in the pharmacy manual.

b In cases of anaphylaxis, epinephrine should be used immediately

Abbreviations: CTCAE = Common terminology criteria for adverse events; IRR = Infusion-related reaction; NCI = National Cancer Institute; NSAIDs: nonsteroidal anti-inflammatory drugs.

Participants who experience cetuximab-related infusion reactions should have cetuximab reduced according to [Table 7](#) and continue to receive antihistamine premedication prior to administration. Once the cetuximab infusion rate has been decreased due to an allergic/hypersensitivity reaction, it should remain decreased for all subsequent infusions. If the participant experiences a second infusion reaction at the decreased rate, cetuximab should be permanently discontinued. If any Grade 3-4 infusion reaction occurs, cetuximab treatment should be discontinued immediately.

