Severe infusion-related reactions, including anaphylactic reactions, may commonly occur, in some cases with fatal outcome. Occurrence of a severe infusion-related reaction requires immediate and permanent discontinuation of cetuximab therapy and may necessitate emergency treatment. Some of these reactions may be anaphylactic or anaphylactoid in nature or represent a cytokine release syndrome (CRS). Symptoms may occur during the first infusion and for up to several hours afterwards or with subsequent infusions.

Table 7 - Cetuximab infusion-related reaction dose modification and treatment guidelines

NCI CTCAE Grade	Dose modification
Grade 1 Mild reaction; infusion interruption not indicated; intervention not indicated	Decrease the cetuximab infusion rate by 50% and monitor closely for any worsening.
Grade 2 Requires therapy or infusion interruption but responds promptly to symptomatic treatment (eg, antihistamines, NSAIDs, narcotics, IV fluids); prophylactic medications indicated for ≤24 hrs	Stop cetuximab infusion and administer bronchodilators, oxygen, etc. as medically indicated. Resume infusion at 50% of previous rate once allergic/hypersensitivity reaction has resolved or decreased to Grade 1 in severity and monitor closely for any worsening.
Grades 3 or 4 Grade 3: Prolonged (ie, not rapidly responsive to symptomatic medication and/or brief interruption of infusion); recurrence of symptoms following initial improvement; hospitalization indicated for other clinical sequelae (eg, renal impairment, pulmonary infiltrates) Grade 4: Life-threatening; pressor or ventilator support indicated	Stop the cetuximab infusion immediately, administer epinephrine, bronchodilators, antihistamines, glucocorticoids, intravenous fluids, vasopressor agents, oxygen, etc., as medically indicated. Cetuximab should permanently discontinued. The participant can continue treatment with SAR444245.

Abbreviations: CTCAE = Common terminology criteria for adverse events; IRR = Infusion related reaction; NCI = National Cancer Institute.

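### Substudy 04, Cohort D2: for a later Grade 2 cetuximab infusion reaction, Table 15 says continue the infusion while the operative Table 7 says stop and resume at half rate

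*Protocol*

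**What the plan says.** All references are to the Protocol, Substudy 04.

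- **Section 6.5.4.1, text.** The instruction opens "Participants who experience cetuximab-related infusion reactions should have cetuximab reduced according to" Table 7. It adds "If the participant experiences a second infusion reaction at the decreased rate, cetuximab should be permanently discontinued". No grade limit is attached to that rule. Section 6.5.4.3 points to Table 7 again for cetuximab infusion reactions.
- **Table 7, Grade 1.** "Decrease the cetuximab infusion rate by 50% and monitor closely for any worsening".
- **Table 7, Grade 2.** "Stop cetuximab infusion and administer bronchodilators, oxygen, etc. as medically indicated", then "Resume infusion at 50% of previous rate once allergic/hypersensitivity reaction has resolved or decreased to Grade 1 in severity".
- **Section 10.11, Table 15, mitigation column for cetuximab.** A reaction in the first 15 minutes of the first infusion means stopping. No grade is named, and a benefit/risk assessment is required before another infusion. After that, "If an infusion-related reaction develops later during the infusion or at a subsequent infusion further management will depend on its severity": "Grade 1: continue slow infusion under close supervision"; "Grade 2: continue slow infusion and immediately administer treatment for symptoms"; at Grades 3 and 4, stop and do not use cetuximab again.
- **First-dose rate.** The Section 1.1 synopsis gives 400 mg/m² over 120 minutes with a maximum of 10 mg/min, and allows local practice and labels to apply instead. Table 15 caps the first dose at 5 mg/min.

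**The concern.** Stop and continue cannot both be followed for the same Grade 2 reaction. A site working from Table 15 would keep running an infusion that Table 7 tells it to interrupt. After a second reaction at the reduced rate, it could keep a participant on a drug that Section 6.5.4.1 says to withdraw. In the first 15 minutes the difference at Grade 1 runs the other way: a site working only from Table 7 would halve the rate where Table 15 says stop. Neither table is therefore the more cautious one throughout.

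What is at stake is consistent handling of mild and moderate reactions in Cohort D2, and consistent cetuximab exposure and discontinuation records. No statistical quantity depends on it.

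**Working it through.** No stated figure needs reproducing for the main point, so the check sets the two texts side by side.

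| Situation | Table 15 | Section 6.5.4.1 and Table 7 | Result |
|---|---|---|---|
| First infusion, first 15 minutes, Grade 1 | Stop; assess benefit/risk before another infusion | Halve the rate | Conflict |
| First infusion, first 15 minutes, Grade 2 | Stop; assess benefit/risk before another infusion | Stop; resume at 50% once resolved or Grade 1 | Agree on stopping only |
| Later or subsequent infusion, Grade 1 | Continue slowly | Halve the rate | Reconcilable, since slow has no number |
| Later or subsequent infusion, Grade 2 | Continue slowly and treat | Stop; resume at 50% once resolved or Grade 1 | Direct conflict |
| Second reaction at the reduced rate, Grade 1 or 2 | Continue slowly (treat at Grade 2) | Discontinue cetuximab permanently | Direct conflict |
| Grades 3 and 4 | Stop, no further use | Stop, discontinue permanently | Agree |

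**How many participants.** Section 2.3.1.2 gives infusion reactions of any grade in 8.4% and Grades 3 and 4 in 2.2% of cetuximab patients in other trials. The difference is 8.4 − 2.2 = 6.2%, or 0.062 × 40 ≈ 2.5 of the 40 planned participants, for the milder grades together. Grade 2 is an unknown part of that. This assumes the historical rate carries over, and Section 2.3.1.3 says the combination may raise it, so the figure is a rough scale and not an upper bound. The section gives timing for severe reactions only (about 90% at the first infusion) and none for Grade 2.

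**Secondary point, first-dose rate.** Inputs: 400 mg/m² and 120 minutes (synopsis), 5 mg/min (Table 15), 10 mg/min (synopsis).

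- Body surface area (BSA) at which 120 minutes just meets a cap = cap × 120 / 400. For 5 mg/min: 5 × 120 / 400 = 1.5 m². For 10 mg/min: 10 × 120 / 400 = 3.0 m².
- Mean rate over 120 minutes = 400 × BSA / 120. The protocol gives no BSA distribution. For an assumed range of 1.6 to 2.2 m²: 5.33 mg/min at 1.6, 6.00 at 1.8, 6.67 at 2.0, 7.33 at 2.2.
- Time needed at 5 mg/min = 400 × BSA / 5 = 80 × BSA: 128 minutes at 1.6 m², 144 at 1.8, 176 at 2.2.

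A 120-minute first infusion thus exceeds Table 15's limit above 1.5 m² and not at or below it.

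**The case against.** The best defence is that the operative rule is not in doubt. Dose modification belongs to Section 6.5.4, which names Table 7 twice. Table 15 is an appendix risk summary that leans on product labelling: just before the grade list it refers treatment of reactions to the country label. Omitting the second-reaction rule from a summary does not cancel it. Table 7 also defines Grade 2 as a reaction that responds promptly to symptomatic treatment, and Table 15 asks for immediate treatment. All of this stands and lowers the severity.

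It does not remove the contradiction. Table 15 words its lines as instructions in the mitigation column and gives no cetuximab reference to Table 7, although the pembrolizumab entry in the same row simply refers to its own Table 5. The Section 6.5.1 rule to take the most conservative recommendation covers several toxicities in one participant, not two texts on one reaction. Investigator discretion under Section 6.5.3 does not reconcile conflicting starting instructions.

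On the rate, the local practice and labels clause lets a site infuse more slowly without breaching the synopsis. The pharmacy manual, which Section 6.1.1 says details administration, is not shown and may settle the matter.

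**Conclusion.** The point holds as an internal contradiction in a safety instruction, of minor to moderate importance. The firm part is the later Grade 2 reaction, together with the missing discontinuation rule. The first-15-minutes difference is also real, reading Table 15's unqualified wording as covering every grade. The rate mismatch is secondary and held with medium confidence, because of the label clause and the manual not seen.

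Three stronger readings are tempting but unsupported:

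- A reader might infer that the contradiction bears on the serious and fatal reactions described in Section 2.3.1.2. The tables agree on Grades 3 and 4, and nothing shown links the Grade 2 difference to more severe outcomes.
- A reader might infer that the 120-minute infusion is unsafe above 1.5 m². No text shown ties rates of 5 to 7 mg/min to more reactions; the finding is only that two limits do not fit.
- A reader might infer that the two tables fully agree on Grade 2 in the first 15 minutes. They agree on stopping, not on whether the infusion may resume.

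The number of participants affected cannot be determined from the documents. Response rate, sample size and decision rules are unaffected.

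**What to change.** 1. In Table 15, replace the cetuximab grade list with a reference to Section 6.5.4.1 and Table 7. This removes the Grade 2 conflict and brings in the second-reaction rule.
2. Put one first-15-minutes rule into Table 7, stating the grades it covers and whether same-day resumption is allowed, and make Table 15 refer to it. Limiting the early stop to Grade 2 and above would not be enough, because the disagreement on resumption would remain.
3. State one first-dose rate limit in both the synopsis and Table 15, after checking the pharmacy manual. If 5 mg/min is kept, require at least 120 minutes and at least 80 minutes per m².

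The sponsor's medical team should choose the early-stop rule and the rate. Keeping the stop at any grade means more interrupted first infusions for mild reactions; keeping 5 mg/min means longer ones (144 minutes at 1.8 m²). The cost is a text correction at the next Substudy 04 amendment and a letter to sites, with no statistical consequence.
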